	the duration of an average ventricular action potential.	• t _{max}	the time to C_{max} during a dosing interval
• QTc	corrected QT interval	• TP	total protein
• QTcB	corrected QT interval using Bazett's formula	• UK	United Kingdom
• RBC	red blood cells	• WBC	white blood cells
• REC	Research Ethics Committee		

GB-HV-01 Clinical Study Protocol
RD 676/25641 Version: FINAL 6.0 / 05 April 2016 Page 19 of 73

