9.7.1.4.3 Vital signs

Vital signs assessments will include: Systolic and diastolic blood pressure, pulse, O_2 saturation, oral temperature and respiratory rate.

Measurements will be recorded in the supine position after 5 minutes (mins) rest. Blood pressure, pulse, O₂ saturation and temperature will be measured using an automated validated device, with an appropriately sized cuff.

9.7.1.4.4 12-lead ECG

12-lead ECG assessments will include: Heart rate, PR interval, QRS width, QT interval, and OTcB interval.

ECGs will be recorded in the supine position after 5 mins rest.

ECG recordings will be made using a MAC 5500 or equivalent. Each ECG trace should be labelled with the study number, subject initials and subject number. An investigator will

Confidential Page 56 of 73

provide an interpretation of each tracing. Clinically significant abnormalities should be recorded on the AE page.

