9.9 Statistical Methods and Determination of Sample Size

9.9.1 Statistical and Analytical Plan

9.9.1.1 Primary and Secondary Variables for Assessment

The primary safety assessment variables will be the vital signs data, ECG data, laboratory data and the adverse events reported.

The secondary pharmacokinetic variables will be the following non-compartmental pharmacokinetic end-points:

	Politica
• C _{max}	Maximum plasma concentration
• t _{max}	The time to maximum observed concentration sampled during
	a dosing interval
 λ_z 	Elimination rate constant
• t _{1/2}	Terminal half-life
• AUC _{0-t}	Area under the plasma concentration-time curve (AUC) from the
	time of dosing to the time of the last observed concentration
• AUC _{0-τ}	Area under the plasma concentration-time curve (AUC) from the
	time of dosing to time t at steady state
• AUC _{0-inf}	The area under the curve (AUC) extrapolated to infinity from dosing
	time, based on the last observed concentration
• CL/F	Plasma clearance, calculated as Dose / $AUC_{0\text{-}inf}$
AUC% extrapolated	Residual area

The secondary pharmacodynamic variables will be the peripheral blood flow cytometry data and galectin-3 plasma concentration data.

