Vital signs parameters will be listed with any out of normal range values flagged. Descriptive statistics of absolute and change from baseline (pre-dose) supine systolic and diastolic blood pressure, supine pulse rate, respiration rate, oral temperature and O_2 saturation at each time point, up to and including Day 15, will be tabulated by dose.

The mean change from baseline data will also be plotted by dose across time, up to and including Day 15.

12-Lead ECG parameters will be listed with any out of normal range values flagged. Descriptive statistics of absolute and change from baseline (pre-dose) heart rate, PR interval, QRS interval, QT interval and QTcB interval at each time point, up to and including day 15, will be tabulated by dose.

Confidential Page 63 of 73

The mean change from baseline data will also be plotted by dose across time, up to and including Day 15.

In addition, frequencies of QTcB data will be calculated according to the following categories:

For absolute values

- OTcB > 450 mSec
- QTcB > 480 mSec
- QTcB > 500 mSec

For change from baseline

- QTcB increase > 30 mSec
- QTcB increase > 60 mSec

All adverse events will be coded using the MedDRA dictionary, version 16.1.

All adverse events, including those that occur prior to the first administration of the study drug, will be listed. Only treatment-emergent adverse events (TEAEs), i.e. existing conditions that worsen or events that occur during the course of the study after administration of study drug, will be included within the summary tables. Adverse event summaries will be presented by treatment and overall (data from all dose groups will be pooled).

An overall summary of adverse events will be produced including the number of TEAEs; the number and percentage of subjects reporting at least one: TEAE, serious TEAE, TEAE leading to withdrawal from the study; the number and percentage of subjects reporting TEAEs by severity and relationship to study drug.

The number of TEAEs and the number and percentage of subjects reporting at least one TEAE will be tabulated by system organ class (SOC) and preferred term (PT). A subject reporting multiple episodes of a particular adverse event within a study period will only contribute one count towards the corresponding system organ class and preferred term within that study period.

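### Bazett's QTcB is the protocol's only corrected QT and the only variable in its outlier categories, so a high resting heart rate alone can put a subject above 450 ms; adding QTcF is a cheap improvement

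*Protocol*

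**What the plan says.** The abbreviations list (protocol section 4) defines QTcB as the "corrected QT interval using Bazett's formula". Section 9.7.1.4.4 sets out what is read from each tracing: "12-lead ECG assessments will include: Heart rate, PR interval, QRS width, QT interval", followed by the QTcB interval. ECGs are taken supine after five minutes' rest, and an investigator interprets each one.

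For the analysis, section 9.9.1.3 summarises absolute values and changes from baseline for "heart rate, PR interval, QRS interval, QT interval and QTcB interval at each time point", with out-of-range values flagged in the listings. It then adds outlier counts: "frequencies of QTcB data will be calculated according to the following categories". The absolute limits are 450, 480 and 500 ms. The change limits are 30 and 60 ms, the first written as "QTcB increase > 30 mSec". All five apply to QTcB, and no other correction is named anywhere in the protocol.

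The status of these data is set in section 9.9.1.1: "The primary safety assessment variables will be the vital signs data, ECG data, laboratory data and the adverse events reported".

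**The concern.** Bazett divides QT by the square root of the RR interval and Fridericia by its cube root. They agree at 60 bpm and separate as the rate moves away from it, with Bazett reading higher above 60 bpm and lower below. A count of subjects over a QTcB limit therefore responds partly to heart rate and not only to repolarisation.

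The counts describe a primary safety variable in very small groups: 4 TD139 subjects per Part 1 cohort and 5 in a Part 2 cohort that is not expanded. One subject over a limit because of a fast resting rate could be read as a possible QT signal at that dose. With 2 placebo subjects per cohort in Part 1 and 3 in Part 2, the placebo column gives little help in telling the two explanations apart. A slow rate works the other way and can keep a subject below a limit.

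This is a method that the protocol states, in both the ECG assessments and the statistical methods. It is not a detail left open for the SAP.

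**Working it through.** The protocol gives no QTc calculation, heart-rate distribution or QT variability, so there is no figure of its own to reproduce. The check asks what heart rate is needed to cross each limit when QTcF does not change.

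**Inputs from the protocol.** Bazett correction (section 4); the five limits (section 9.9.1.3); group sizes (section 9.1).

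**Inputs assumed.** QTcF of 400 to 430 ms and a starting heart rate of 60 bpm. Holding QTcF constant makes it the reference for no repolarisation change. That is a convention of this check, not something the protocol states.

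**Formula.** With RR = 60/HR, QTcB = QT/RR^(1/2) and QTcF = QT/RR^(1/3), so QTcB = QTcF × (HR/60)^(1/6).

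**Absolute limit of 450 ms.** Setting QTcB = 450 gives HR = 60 × (450/QTcF)^6.

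| Constant QTcF (ms) | HR at which QTcB reaches 450 ms (bpm) |
|---|---|
| 430 | 78.8 |
| 420 | 90.8 |
| 410 | 104.9 |
| 400 | 121.6 |

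As a worked value, 420 × (95/60)^(1/6) = 453.4 ms.

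**Increase of 30 ms.** Starting from 60 bpm, where QTcB = QTcF, HR = 60 × ((QTcF + 30)/QTcF)^6.

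| Constant QTcF (ms) | HR needed (bpm) | Rise from 60 (bpm) |
|---|---|---|
| 400 | 92.6 | 32.6 |
| 410 | 91.7 | 31.7 |
| 420 | 90.8 | 30.8 |
| 430 | 89.9 | 29.9 |

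So 410 ms going from 60 to 95 bpm gives +32.6 ms. At 90 bpm the increase is 28.0 ms for 400 ms and 29.4 ms for 420 ms, just short of the limit. A smaller rise contributes part of it: 410 ms going from 60 to 70 bpm reads 420.7 ms, which is +10.7 ms and leaves 30 − 10.7 = 19.3 ms to come from ordinary QT variability.

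**Higher limits.** At QTcF 420 ms, both 480 ms and a 60 ms increase from 60 bpm need 133.7 bpm. At QTcF 430 ms, 480 ms needs 116.1 bpm. The 500 ms limit needs still higher rates. None of these is a plausible resting rate.

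**Opposite direction.** At 50 bpm the factor is (50/60)^(1/6) = 0.970, so any QTcF up to 450/0.970 ≈ 464 ms reads as 450 ms or less by QTcB.

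**Simulation under assumptions.** One million draws per scenario with no true QT effect: QTcF mean 400 or 410 ms, between-subject SD 17, within-subject SD 8; heart-rate mean 60 to 80 bpm, between-subject SD 9, within-subject SD 5 to 8.

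| Event per post-baseline ECG | QTcF | QTcB, no HR shift | QTcB, HR shift +10 bpm |
|---|---|---|---|
| Above 450 ms | 0.4-1.7% | 1.1-18% | 3-30% |
| Increase above 30 ms | about 0.4% | 1.3-4.0% | 5-13% |

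The width of the ranges shows how strongly the size depends on the assumed heart rate. The direction follows from the formula when rates lie mostly above 60 bpm.

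**Weight of one outlier.** 1/4 = 25% in Part 1, 1/5 = 20% in a Part 2 cohort, and 1/8 = 12.5% in a Part 2 cohort expanded by 3 TD139 subjects.

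**The case against.** The case against acting is substantial, and much of it stands.

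- **QT is not assessed by Bazett alone.** A reader might infer that it is. In fact heart rate and uncorrected QT are listed and summarised, mean changes are plotted by dose, and an investigator interprets each tracing. Only the corrected value and the five outlier counts are confined to QTcB. The by-dose summaries do not reclassify an individual subject, though; that has to be done by hand from the listings.
- **No formal decision depends on QTc.** None of the stopping criteria in section 9.2.3 uses it. A clinically significant drug-related event can stop dosing, and ECG data are among those reviewed at escalation, but both routes go through judgement and not through a QTcB count.
- **The 30 ms example is demanding.** About 30 bpm is a large change between supine resting recordings if QTcF is constant. The introduction (section 7) reports no significant change in ECG or vital signs up to 10 mg, and nothing in the protocol suggests that TD139 alters heart rate.
- **The arithmetic shows that two formulas differ.** It takes a constant QTcF as the reference and does not prove Fridericia right. This stands, and it is why the proposal is to show both corrections and not to replace one with the other.
- **Nothing is foreclosed.** QT and heart rate are recorded, and the SAP, which is not at hand, could add a second correction. A reader might also infer that they are collected for that purpose; the protocol gives no such purpose and merely makes it possible.

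**Conclusion.** The point holds as a cheap improvement of low severity. The protocol fixes one rate correction and ties every QT outlier count to it. The 450 ms category is the exposed one: heart rate alone can cross it at about 79 bpm for a QTcF of 430 ms and about 91 bpm for 420 ms. The 30 ms category is less exposed, since it takes a rise of about 30 bpm from 60 bpm or a smaller rise combined with ordinary QT variability. The 480, 500 and 60 ms categories are practically unaffected at rest.

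These results rest on a constant QTcF as the reference and on assumed heart rates; the simulated percentages also rest on assumed variability. A reader might go further and conclude that the planned counts will produce a false QT signal, or that escalation or stopping would be misdirected. The documents do not support that: they contain no heart-rate effect, the ECG analysis is descriptive, and no stopping criterion is expressed in QTc. What remains is that one ambiguous outlier weighs heavily in groups of 4 to 8 TD139 subjects, and the planned tables would not show whether it survives a second correction.

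**What to change.** In the ECG paragraph of section 9.9.1.3, add QTcF as a variable derived from the recorded QT and heart rate in both Parts. Tabulate it in the same five categories beside QTcB, and state that any QTcB outlier will be interpreted together with that subject's QTcF and heart rate at the same time point.

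The cost is one derived variable and one further table, with no new ECGs. The downside is a second set of descriptive counts in small groups that may disagree with the first; the sentence on joint interpretation is there to say in advance how a disagreement will be read.

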9.7 Efficacy and Safety Variables

9.7.1 Efficacy and Safety Measurements Assessed and Flow Chart

Pre-study screening assessments will be carried out in the 28 day period before the first dose.

In **Part 1** post-study assessments will be carried out 12-16 days after the final study procedure on day 14.

In **Part 2** post-study assessments will be carried out 26 - 30 days after the last day of the Study Period.

All study personnel who have been appropriately trained will carry out study procedures.

The Study Flow Chart is provided in Table 9.7.1 and Table 9.7.2.

Where more than one procedure is scheduled for the same time-point, the following order of priority will apply:

- 1. PK and PD blood sampling (a window of \pm 2 min in relation to the nominal time-point is allowed)
- 2. Vital signs and 12-lead ECG (a window of \pm 10 min in relation to the nominal time-point is allowed. A window of \pm 30 mins will apply to the Day 14, 2h time point in Part 2 to fit around the BAL sampling procedure).

All pre-dose/baseline assessments may be performed within the 30 mins before dosing.

Confidential Page 47 of 73

Table 9.7.1 Part 1 Study Flow Chart

Visit	g .	Treatment Period							
	Screening		In-house			Post Study			
Day (h)	(Day -28 to -2)	Day -1	Day 1	Day 2 (24h)	Day 3 (48h)	Day 8 (168h)	Day 14 (312h)	(Day 26-30)	
Informed consent	X								
Inclusion/Exclusion	X	X							
Demographics	X								
Height / Weight / BMI ¹	X							X	
Medical History & Concurrent Conditions	X								
Biochemistry Haematology Urinalysis	X	X	X ²	X				X	
Virology	X								
Drugs of Abuse	X	X							
12-Lead ECG	X	X	X ³	X		X	X	X	
Physical Examination	X							X	
Vital Signs ⁴	X	X	X ⁵	X	X	X	X	X	
Spirometry (FEV1 & FVC)	X								
Dose			X						
PK Blood Sampling			\mathbf{X}^{6}	X	X				
PG & Flow Cytometry sampling		X	X ⁷	X				X	
Galectin-3 Blood sampling		X	X ⁸		X			X	
Exhaled Breath Condensate		X	X ⁹					X	
Adverse Events		+					·	—	
Concomitant Medication	X	4						—	

GB-HV-01 Clinical Study Protocol Confidential RD 676/25641 Version: FINAL 6.0 / 05 April 2016 Page 48 of 73

Table 9.7.1 Study Flow Chart Footnotes:

- 1. Height at Screening Visit only.
- 2. Laboratory safety samples will be taken at 6h post-dose.
- 3. 12-lead ECG to be measured prior to dosing = 0h and then at 30min and 2h post-dose.
- 4. Blood pressure, pulse, O₂ saturation, oral temperature, respiratory rate.

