- 5. Vitals signs will be recorded prior to dosing = 0h and then at 5min, 15min, 30min, 2h, and 6h post-dose.
- 6. PK blood sampling will be taken prior to dosing = 0h and then at 15min, 30min, 45min, 1h, 2h, 3h, 4h, 5h, 6h, 12h and 18h post-dose.
- 7. Blood sampling for pharmacogenetic analysis (mRNA) and peripheral blood flow cytometry will be taken prior to dosing = 0h and then at 30min, 2h and 18h post-dose.
- 8. Blood sampling for Galectin-3 analysis will be taken prior to dosing = 0h and then at 5h post-dose.
- 9. Exhaled Breath Condensate will be taken prior to dosing = 0h and then at 1.5h post-dose.

Confidential Page 49 of 73

Table 9.7.2 Part 2 Study Flow Chart

Visit	Screening	Treatment Period						Post Study
Day	(Day -28 to -2)	Day -1	Day 1-3	Day 4-6	Day 7	Day 8-13	Day 14-15	(Day 41-45)
Clinic Visits	X	X	X		X		X	X
Informed consent	X							
Inclusion/Exclusion	X	X						
Demographics	X							
Height / Weight / BMI ¹	X							X
Medical History & Concurrent Conditions	X							
Biochemistry, Haematology, Urinalysis	X	X	X ²				X ²	X
Pregnancy Test	X							
Virology	X							
Drugs of Abuse	X	X						
12-Lead ECG	X	X			X^3		X^3	X
Physical Examination	X							X
Vital Signs ⁴	X	X	X ⁵		X^5		X ⁵	X
Spirometry ⁶	X						X ⁷	X
DLCO	X							
Dose ⁸			X	X	X	X	X	
PK Blood Sampling			X ⁹		X ⁹		X ⁹	
PG & Flow Cytometry Sampling			X ¹⁰		\mathbf{X}^{10}		X ¹⁰	
PBMC analysis			X ¹¹				X ¹¹	
Galectin-3 Blood sampling		X	X ¹²		X ¹¹		X ¹²	X
Exhaled Breath Condensate		X					X ¹³	X
Bronchoalveolar Lavage		X ¹⁴					X ¹⁴	
Adverse Events		•						
Concomitant Medication	X	◆						—

GB-HV-01 Clinical Study Protocol Confidential RD 676/25641 Version: FINAL 6.0 / 05 April 2016 Page 50 of 73

Table 9.7.2 Study Flow Chart Footnotes:

- 1. Height at Screening Visit only.
- 2. Laboratory safety samples will be taken on Day 1 at 6h post-dose, on Day 3 (prior to dosing) and Day 14 at 6h post-dose.
- 3. 12-lead ECG to be measured on Day 7 and Day 15.
- 4. Blood pressure, pulse, O₂ saturation, oral temperature, respiratory rate.
- 5. Vitals signs will be recorded on Day 1 prior to dosing = 0h and then at 5min, 15min, 30min, 2h, and 6h post-dose; Day 2, 3 and 7 prior to dosing = 0h; Day 14 prior to dosing = 0h and then at 5min, 15min, 30min, 2h, and 6h and 24h post-dose. (A window of ± 30 mins will apply to the Day 14, 2h timepoint in Part 2 to fit around the BAL sampling procedure)
- 6. Spirometry measurement to be recorded at equivalent time at each timepoint (\pm 1h).

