In addition, the number and percentage of subjects reporting TEAEs will be tabulated by maximum severity and strongest relationship to study drug. For the summary of TEAEs by severity, if a subject has multiple events occurring within the same SOC or preferred term, the event with the highest severity will be counted. Similarly, for TEAEs by relationship to study drug, if a subject has multiple events occurring within the same SOC or preferred term, the event with the highest association to study drug will be counted.

Biochemistry, haematology and urinalysis parameters will be listed with any out of normal range values flagged. Laboratory test results that are out of normal range will also be presented separately along with normal reference ranges. Descriptive statistics of absolute and change from baseline (pre-dose) values for each biochemistry and haematology parameter at each time point, up to and including day 15, will be tabulated by dose.

GB-HV-01 Clinical Study Protocol Confidential RD 676/25641 Version: FINAL 6.0 / 05 April 2016 Page 64 of 73

Frequencies of the total number of subjects randomised, completed, and prematurely discontinued (including reason for discontinuation) from the study will be summarised by dose. Additionally the frequency of subjects within each analysis population (safety, PK) will be summarised by dose.

Demographic data will be listed and descriptive statistics will be tabulated for the continuous variables age, height, weight and BMI and frequencies for the categorical variable race. These descriptive statistics will be presented by dose and overall.

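### The by-dose tables of vital signs, ECG and laboratory data stop at Day 15, so the post-study visit is collected but not summarised by dose

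*Protocol*

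**What the plan says.** Under the safety assessments in protocol Section 9.9.1.3, three sets of by-dose descriptive tables (absolute values and change from baseline) have a last day fixed in the text:

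- Biochemistry and haematology: statistics "for each biochemistry and haematology parameter at each time point, up to and including day 15, will be tabulated by dose".
- Vital signs: statistics "at each time point, up to and including Day 15, will be tabulated by dose".
- ECG: the limit covers "QRS interval, QT interval and QTcB interval at each time point, up to and including day 15, will be tabulated by dose".

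The mean-change plots for vital signs and ECG also end at Day 15. No reason is given.

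The schedule in Section 9.7.1 goes further. Tables 9.7.1 and 9.7.2 mark laboratory tests, ECG and vital signs at a post-study visit, Day 26-30 in Part 1 and Day 41-45 in Part 2. For Part 1 the text adds that "post-study assessments will be carried out 12-16 days after the final study procedure on day 14". The laboratory footnotes read, for Part 1, "Laboratory safety samples will be taken at 6h post-dose" (on Day 1) and, for Part 2, "Laboratory safety samples will be taken on Day 1 at 6h post-dose, on Day 3 (prior to dosing) and Day 14 at 6h post-dose".

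Other outputs in Section 9.9.1.3 have no Day 15 limit: the listings of all vital sign, ECG and laboratory values with out-of-range flags, the separate presentation of out-of-range laboratory results, the QTcB category frequencies and the treatment-emergent adverse event tables.

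**The concern.** Section 9.9.1.1 names vital signs, ECG, laboratory data and adverse events as the primary safety variables, and safety is the primary objective of both parts. The planned analysis of the first three is descriptive, so the by-dose table of change from baseline, with placebo alongside, is the main summary a reader will use. A visit left out of it gets no by-dose summary of whether a change recovered or appeared late.

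The treatment of a secondary variable makes the omission look unintended. Galectin-3 plasma levels are also sampled post-study in both parts, and Section 9.9.1.3 has them summarised at every time point by dose with no last day. The plan would therefore summarise the post-study visit for a secondary pharmacodynamic marker but not for the primary laboratory, ECG and vital sign variables. The synopsis, which describes tabulation of safety parameters by treatment group, also sets no time limit.

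**Working it through.** No power, sample size or error-rate figure is involved. The check applies the Day 15 limit to each scheduled post-dose time point.

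**Visit windows.**
- Part 1: Day 14 + 12 = Day 26 and Day 14 + 16 = Day 30, matching the heading of Table 9.7.1.
- Part 2: taking Day 15 as the last day of the study period, Day 15 + 26 = Day 41 and Day 15 + 30 = Day 45, matching Table 9.7.2.

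Both windows lie wholly after Day 15.

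**Post-dose time points, from the flow charts and their footnotes.**

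| Assessment | Scheduled on or before Day 15 | Tabulated / scheduled |
|---|---|---|
| Part 1 laboratory | 6 h, 24 h | 2 of 3 |
| Part 2 laboratory | Day 1 6 h, Day 3 pre-dose, Day 14 6 h | 3 of 4 |
| Part 1 ECG | 30 min, 2 h, Day 2, Day 8, Day 14 | 5 of 6 |
| Part 2 ECG | Day 7, Day 15 | 2 of 3 |
| Part 1 vital signs | five times on Day 1, then Days 2, 3, 8, 14 | 9 of 10 |
| Part 2 vital signs | five on Day 1; Days 2, 3, 7; seven from Day 14 pre-dose to 24 h | 15 of 16 |

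In every row the one omitted point is the post-study visit.

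**What the omitted laboratory point is.**
- Part 1: the laboratory cells for Days 3, 8 and 14 in Table 9.7.1 are empty, so the tables end at 24 h. The omitted value falls 26 - 1 = 25 to 30 - 1 = 29 days after the single dose.
- Part 2: fourteen daily doses from Day 1 end on Day 14. The omitted value falls 41 - 14 = 27 to 45 - 14 = 31 days after the last dose and is the only off-treatment laboratory value. The last tabulated value, 6 h after the Day 14 dose, also follows that day's lavage. The lavage is scheduled 1 to 4 h after the dose, so the sample comes 6 - 4 = 2 to 6 - 1 = 5 h after it.

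**After the change.** Laboratory tables go from 2 to 3 post-dose points in Part 1 and from 3 to 4 in Part 2. ECG goes from 5 to 6 and from 2 to 3. Vital signs go from 9 to 10 and from 15 to 16.

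**The case against.** The limit can be defended as a choice of presentation. Both flow charts separate the treatment period from the post-study visit. Day 15 is the last treatment-period day in Part 2, and Day 14 is the last in Part 1. Summarising the treatment period and listing the follow-up is coherent, and the protocol nowhere promises a by-dose post-study summary.

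The practical harm is also limited:

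- Listings cover every value, including those within range. With 4 active subjects per Part 1 cohort and 5 per Part 2 cohort (8 if expanded), individual courses can be read directly, and a mean over so few is a weak detector of drift.
- Clinically significant laboratory and ECG abnormalities are to be recorded as adverse events (Sections 9.7.1.4.2.1 and 9.7.1.4.4), and those tables are not cut.
- No trial decision depends on these tables. Part 1 escalation uses data to Day 3, and the stopping criteria use adverse events and exposure.
- The Part 1 laboratory gap after 24 h comes mainly from the sampling schedule. Lifting the limit adds one value. If the human half-life resembles the roughly 6 h reported for animals in Section 9.6.7, that value comes 25 x 24 / 6 = 100 to 29 x 24 / 6 = 116 half-lives after the dose. It can show recovery or a lasting change but does not fill the interval between.

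All of this stands, and it sets the severity. It does not explain why the visit is left out of the by-dose summaries of primary variables while it remains in those for galectin-3. Listings also do not fully replace a summary. A within-range shift is neither flagged nor set against placebo by dose, and in Part 2 the flags rest on local reference ranges at four centres.

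**Conclusion.** The point holds as a minor gap in reporting. The stated limit leaves exactly one scheduled visit, the post-study visit, out of the by-dose tables for vital signs, ECG, biochemistry and haematology, and out of the vital sign and ECG plots. It matters most for laboratory data, where Part 1 tables end at 24 h and Part 2 tables contain no off-treatment value.

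Three stronger readings are tempting, and the protocol does not support them:

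- That all safety tables stop at Day 15. Adverse event tables cover events throughout the study after dosing.
- That a late within-range shift would be visible nowhere. The limit removes one visit from the tables, not the tables themselves, and every value is still listed.
- That the QTcB category counts exclude the visit. No last day is stated for them.

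The conclusion rests on reading the Day 15 wording literally and on the flow-chart cells as printed. With groups this small the added summaries would be descriptive only.

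**What to change.** In Section 9.9.1.3, replace the Day 15 limit with the post-study visit as the last time point for the vital sign, ECG, biochemistry and haematology tables, and for the vital sign and ECG mean-change plots. The QTcB category counts need no change.

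The cost is one additional visit in existing tables and plots. The data are already scheduled and collected, and no assessment, dose or decision rule is affected. If the sponsor prefers to keep the main tables to the treatment period, a separate by-dose summary of change from baseline at the post-study visit would close the same gap.
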